5.5 Describe the procedure for obtaining intervention group assignment

The study coordinator with the statistician will randomize participants stratified by MCI status. Participants with and without MCI will be randomized in a 1:1 ratio to either piano training or the active control condition of music listening instruction. To ensure balance throughout enrollment, randomization will be stratified by MCI status (present vs. absent) and conducted in varying blocks of participants as designed by Co-I Ji. [name] will generate the stratified permuted random blocks using R. [name] will maintain the random seed and the computer codes and will send the randomization list to the clinical trial coordinator. The treatment allocation will be denoted as A or B and recorded on the randomization form by the clinical trial coordinator. The study coordinator will control access to the randomization list and know whether A (B) stands for intervention (control). Study investigators [name], [name], and [name] will remain blind to participant condition. The testers will remain blind to participant condition. The trainers (including Co-I [name]) and clinical trial coordinator will be aware of participants' randomized condition.

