5.3 Enrollment Procedures

Participants will primarily be recruited through the community, the Cognitive and Neurophysiology of Aging Lab registry, and mailing list of older adults residing in the area. We may also use the Byrd Alzheimer's Institute Community-Based Memory Screening program and the Department of Psychiatry and Behavioral Neurosciences Memory Disorders Clinic (MDC) to enroll participants in the study.

Recruitment and enrollment will occur across a pilot and five or six replicates. Pilot replicate data will only be included in interim or final analyses if no significant changes to the study procedures or this protocol are made after the pilot replicate is completed. Any changes to the protocol will be noted with the effective date and justification.

Throughout the study period at least one Research Assistant in the Cognitive and Neurophysiology of Aging Lab will make recruitment phone calls and answer potential participant emails/calls. Individuals who have expressed interest in our research will be telephone screened (i.e., inclusion/exclusion questionnaire) by lab staff. The study script should be followed for describing the study and answering any participant questions. Screeners will emphasize to the participants that they are committing to complete up to 23 in-person study visits (i.e., 3 testing sessions and 20 intervention sessions) over the next five months. Once eligibility and interest has been assessed, the final outcome is coded. The final recruitment outcome will be coded as 1) Scheduled; 2) Not Scheduled and Will Not Try Again; or 3) Not Scheduled, Will Try Again.

If the participant is not eligible because they are planning on being away or unavailable for more than 2 weeks in the next 5 months, or are planning on having major surgery or undergoing any type of anesthesia, chemotherapy, or radiation treatment in the next 5 months, we will attempt to recruit them for the next replicate.

The study coordinator will oversee recruitment and serve as a primary contact for study participants.

Those deemed initially eligible from telephone screening will complete an in-person screening at the Cognitive and Neurophysiology of Aging Lab. This in-person screening will include the Montreal Cognitive Assessment (MoCA), Geriatric Depression Scale, vision and hearing screenings as well as the Music Reading Assessment (MRA) to further confirm eligibility (See Inclusion/Exclusion above for details).

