Those potentially eligible based on completion of these measures will further complete baseline cognitive, CAP, and everyday functional measures.

Those eligible who score 26³ or better on the MoCA will be enrolled in the study and referred to the study coordinator for randomization.

Those potentially eligible who score between 20 to 25 on the MoCA who were not referred by the MDC or study physician will also complete a clinical evaluation visit. A cut-point of 20-25 on the MoCA is indicative of probable MCI, while less than 20 is suggestive of dementia⁸⁸.

³ The MoCA cutpoint was changed from 27 to 26 to use the more traditional and accepted value for impairment. Those who score between 20 to 25 will complete the clinical evaluation, rather than those who score 20 to 26.

The purpose of the clinical evaluation is to determine if participants have MCI or dementia. The clinical evaluation visit will include subtests of the National Alzheimer's Coordinating Center Uniform Data Set (NACC) neuropsychological battery and an exam by a study physician. Subtests of the NACC battery will be used to determine MCI status and exclude dementia. The NACC battery subtests to be administered include the Clinical Dementia Rating Scale, the Multilingual Naming Test, the Benson Complex Figure Copy immediate and delayed subtests, the Craft Story 21 immediate and delayed recall subtests, Functional Assessment Scales, and Clinical Diagnosis Form, completed by a study physician who is a geriatric psychiatrist.

An exception to the above procedure will be for patients with MCI who were referred from the USF Health Memory Disorders Clinic (MDC) or a study physician who have already undergone clinical evaluation in the past 6 months. Eligible and enrolled participants referred from the clinic with prior MCI diagnosis and evaluation in the clinic completed within the past 6 months will be referred to study coordinator for randomization.

In replicate 1 and later replicates, we plan to request lab results from the past year from those who score 20-25 on the MoCA. The purpose is to rule out medical causes of cognitive decline that are treatable. If copies of lab results are not obtained at the baseline visit, we will request that the participant complete a release of medical records. If we do not receive medical records by the clinical evaluation, and the study physician recommends it, we may draw blood and order lab tests that may include:

- CBC
- Metabolic panel

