6.1.2 Intervention Phase

Within three weeks of baseline or clinical evaluation phase completion for each replicate, the Clinical Research Coordinator and/or Research Assistant Trainers will randomize enrolled participants in collaboration with [name] and schedule their first intervention visit. Participants will complete randomized exercises in groups of up to 10 individuals at in-lab sessions that are 90 minutes in duration, occurring two times a week over the subsequent ~3 months. The goal will be for 95% of the training sessions to be conducted in groups of 3-10 persons. Clas-

ses will be arranged such that those with MCI primarily train together within randomized condition. The intervention phase will continue until 20 total sessions are completed or 15 weeks have passed. The trainers will confirm or reschedule the participant to complete an immediate post-intervention assessment. The trainers will make certain that all scheduled intervention sessions are completed prior to the post-test visit and that no training sessions are scheduled after the post-test visit. Fidelity will be assured as described below (See **Quality Assurance** below).

At the first training sessions the trainers will administer the Advanced Measure of Music Audiation (AMMA), General Self-Efficacy Form, and the Music Performance Self-Efficacy form. Those in the music listening control group will complete the music listening measure while those in piano training will complete the basic piano measure. The training protocols detail all of the procedures and content protocols detail the training arms. Please see: P:\CBCS\CSD CAL\Study 15 Music Training NIA\Trainer Docs\Study 15 Music Training procedure protocol.

Between sessions 17 and 20, the trainers will administer the The Cognitive Training Expectations NICT questionnaire to examine participants' attitudes and expectations about the potential effects of the intervention completed. If a participant does not complete this questionnaire during the intervention phase, it may be completed at the beginning of the post-test visit.

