The randomized groups did not differ in sex, $\chi^2(1)=.787, p=.375$, ethnicity $\chi^2(1)=.167, p=.683$, or race, $\chi^2(1)=.045, p=.832$. The Music Reading Assessment scores did not differ between the two groups, $t(266)=-.958, p=.338$. The randomized groups did not significantly differ in age, $F(1,266)=.293, p=.589$, education, $F(1,266)=.369, p=.544$, MoCA, $F(1,266)=.427, p=.514$, or GDS, $F(1,266)=.943, p=.332$. However, there were marginally significant group differences for PTA in the left ear, $F(1,266)=3.31, p=.070$ and statistically significant group differences for both PTA in the right ear, $F(1,266)=6.69, p=.010$, and visual acuity, $F(1,266)=8.99, p=.003$. The music listening group tended to have worse hearing, while the piano training group tended to have worse visual acuity. See Table 1. The groups also differed significantly in their expectations regarding potential benefits of their randomized group, $F(1,214)=15.07, p<.001$. The piano training group had an average rating of 5.55 while the music listening group had an average rating of 4.99, indicating the piano training condition had higher expectations about the potential effects of their randomized condition. The piano training group also rated their condition as more challenging with 92% agreeing that the intervention was challenging as compared to 86.3% of the music listening group indicating their condition was challenging ($p<.001$).

Principal component analysis with varimax rotation was conducted to reduce the number of variables for analyses. Please see Supplemental Table A for details. The first factor reflected cognitive performance speed and included the Trail Making Test, Digit Coding, and the TEA visual elevator and phone search subtests. The second factor included all three verbal fluency subtests. The third factor reflected CAP and included DDT, DSI, TCS, and WIN. The fourth factor included two indices from the TEA phone search while counting and visual elevator accuracy. The fifth composite included ATTR across- and within- channel performance. Baseline composites of cognitive performance, verbal fluency, ATTR, CAP, and everyday function were created by averaging z scores after the reverse-scaling of items with negative factor loadings. Post-test scores were standardized

by baseline means and *SDs*. Timed IADL performance did not significantly load on any factor and was thus examined separately.

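### Upcoming assignments are not secured from the study coordinator, who oversees recruitment and holds the decoded randomisation list

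*Combined protocol and SAP*

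**What the plan says.** Four parts of the protocol bear on this.

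- **Recruitment (Section 5.3).** "The study coordinator will oversee recruitment and serve as a primary contact for study participants". Eligible people with a MoCA score at or above the cut-point "will be enrolled in the study and referred to the study coordinator for randomization". Participants referred from the memory clinic with a recent MCI evaluation are also sent to the coordinator for randomisation.
- **Custody of the list (Section 5.5).** The person who generates the stratified permuted blocks keeps the seed and code and "will send the randomization list to the clinical trial coordinator". Then: "The study coordinator will control access to the randomization list and know whether A (B) stands for intervention (control". Allocation is 1:1 within MCI stratum, in blocks of varying size; the sizes are not given. Testers and three investigators stay blind. Trainers and the clinical trial coordinator know participants' conditions.
- **Who randomises, first statement (Section 5.5).** "The study coordinator with the statistician will randomize participants stratified by MCI status".
- **Who randomises, second statement (Section 6.1.2).** "the Clinical Research Coordinator and/or Research Assistant Trainers will randomize enrolled participants in collaboration with" (the name that follows is removed in the public text). The step is timed by replicate, no more than three weeks after the baseline or clinical phase ends.

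I found no description of a concealed release step: no central or web-based release, no sealed envelopes, and no custodian separate from recruitment.

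**The concern.** Random generation of a sequence protects a trial only if the people who can influence entry, or the matching of people to list positions, cannot see what comes next. Here the role that oversees recruitment and is a main contact for participants also controls the sequence and can decode it. If the list holder knows that the next position in the MCI stratum is piano, nothing in the plan stops that position from going to one enrolled person rather than another.

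No bad intent is needed. Under Section 5.7 the trainers or the study coordinator schedule classes of up to 10 by condition, and Section 6.1.2 wants participants with MCI to train mainly together within condition. Staff may therefore have practical reasons to think about who goes where.

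What is at stake is selection bias in the piano versus listening contrast. The intent-to-treat analysis keeps people in the arm to which they were assigned; it cannot correct the way in which the assignment was made.

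**Working it through.** The plan states no figure on this point, so the check is mainly a comparison of sections.

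**1. Does one role combine recruitment and knowledge of the sequence?** Yes. Section 5.3 gives the study coordinator oversight of recruitment and receipt of enrolled participants. Section 5.5 gives the study coordinator control of list access and the A/B key. The documents use three titles (study coordinator, clinical trial coordinator, Clinical Research Coordinator). They appear to be one role, but this is not stated. The finding does not depend on it, because both statements just cited name the study coordinator.

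**2. Does the A/B label mask anything from this role?** No. Section 5.5 says that the role knows what the letters stand for.

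**3. Is the matching of people to list positions fixed?** No section says so. Randomisation takes place by replicate, after the baseline or clinical phase, so several enrolled people may be waiting in a stratum at once. The plan does not say that they are taken in order of enrolment or of baseline date, or in any other set order.

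**4. Do varying block sizes help?** Only against guessing. Take an observer who cannot see the list but knows the block size and past assignments, and who always guesses the arm with more places left in the block. The block sizes are my assumption.

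- Block of 2: the first guess is right with probability 1/2 and the second is certain. (0.5 + 1)/2 = 0.75.
- Block of 4: the expected correct guesses by position are 1/2, 2/3, then (2/3)(1/2) + (1/3)(1) = 2/3, then 1. (0.5 + 0.667 + 0.667 + 1)/4 = 0.708.
- Blocks of 6 and 8, by the same enumeration: 0.683 and 0.666.

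Varying the block size makes such guessing harder. A person who holds the list and the key does not guess and knows the next assignment every time, whatever the block size.

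**5. Do the two statements on who randomises agree?** No. Section 5.5 names the coordinator with the statistician. Section 6.1.2 names the coordinator and/or the trainers, with a colleague who may or may not be the statistician. If that colleague is the statistician, the conflict narrows to whether trainers take part.

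**6. What else remains open at the time of assignment?** Section 5.1 includes a criterion that rests on the opinion of the tester and of other personnel who interact with the participant. Section 6.1 allows missing baseline or clinical measures to be completed after randomisation, as long as training has not begun. Neither is a fault in itself, but each means that entry data are not necessarily closed when the assignment is made.

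**The case against.** The case on the other side is substantial.

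- **Others control entry.** Lab staff screen by telephone, Research Assistants take consent, blind testers do the baseline assessments, and physicians decide eligibility at the clinical evaluation. A reader might infer that those who admit participants can see the list. The documents do not say so, and enrolment comes before referral for randomisation. This stands, and it limits the finding to the coordinator.
- **The statistician is involved.** Section 5.5 has the coordinator randomise with the statistician. This helps only if the plan says who releases what, and when; it does not.
- **Timing and extent of the list.** The text does not say when the list is sent, or whether it covers the whole trial or one replicate. A claim that the full list was sent in advance would go beyond the text.
- **Trainers are not described as recruiting.** This stands. Their mention in 6.1.2 matters mainly as a contradiction with 5.5.
- **Class times are flexible.** Section 6.3.1 offers make-up and Saturday sessions, and classes are formed by randomised condition. Pressure from scheduling is possible but not described.
- **The analysis adjusts.** Section 9.6 adds baseline variables that differ at p < .1 and tests change from a measured baseline. This reduces the concern for measured factors and leaves the unmeasured ones.

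A stronger reading is also tempting. Section 14 reports "statistically significant group differences for both PTA in the right ear" (p = .010) and for visual acuity (p = .003), and a reader might take this as a sign that allocation was subverted. It does not support that. The section gives 11 comparisons of baseline characteristics. If they were independent, two or more would reach p < .05 with probability 1 − 0.95^11 − 11 × 0.05 × 0.95^10 = 1 − 0.569 − 0.329 = 0.102. A stricter cut-off makes the result look rarer, but only because it is chosen after seeing the p-values. The imbalances also run in opposite directions (worse hearing in the listening arm, worse vision in the piano arm), and age, education, MoCA and GDS are balanced (p = .332 to .589). No probability of this kind should be used as evidence here.

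**Conclusion.** The concern holds in a limited form. As written, the plan does not secure upcoming assignments from the study coordinator, and it gives two different accounts of who randomises. This rests on the stated custody rule in Section 5.5 together with the recruitment role in Section 5.3, and on the absence of any rule that fixes entry order.

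The size of any resulting bias cannot be derived from the documents, and no sample size or power figure changes. Randomisation after enrolment and blind outcome testers reduce the exposure. What remains is the matching of enrolled people to known positions within a replicate and, less directly, influence on the opinion-based eligibility criterion.

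It would be too strong to say that allocation was not concealed from anyone who enrolled participants, or that it was in fact manipulated; the documents show neither. The point is worth acting on because the remedy is cheap and because, without a documented procedure, the sponsor cannot readily rule the problem out.

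**What to change.** - **Section 5.5.** State that the statistician keeps the list and the A/B key. Once eligibility, MCI stratum and baseline are complete, the coordinator submits a locked list of IDs in enrolment order, and the statistician then returns the assignments. Any measure that Section 6.1 allows to be collected later should be flagged on the locked list.
- **Section 6.1.2.** Delete the option for Research Assistant Trainers to randomise, so that it agrees with 5.5. Use one title for the coordinator throughout, or say that the titles denote different people.
- **For this trial.** Data collection was completed in April 2021 (Section 14), so new wording cannot change the allocation. The sponsor should state the procedure actually used: who held the list, when it was sent, how entry order was set, and whether trainers took part. Assignment order should be checked against enrolment order, using the retained seed and code and the randomisation forms described in Section 5.5.

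The cost is a few sentences of protocol text and one exchange of messages between staff already involved. The downside is a short delay, which fits within the minimum of two weeks that Section 6.2 already reserves between the baseline/clinical phase and training. The retrospective check needs only records that the plan says are made or kept.

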5.6 STUDY INTERVENTIONS

5.7 Interventions, Administration, and Duration

There are two arms in this study including group piano training (intervention) and music listening instruction (active control). Both of these arms are described to participants as “music training”. The detailed procedural protocol for both training arms can be found here: P:\CBCS\CSD CAL\Study 15 Music Training NIA\Trainer Docs\Study 15 Music Training Procedure Protocol.... or upon request to the PI.

The content protocol for the **piano training** arm can be found here P:\CBCS\CSD CAL\Study 15 Music Training NIA\Trainer Docs\Piano training Manual_JB_Copyright_2018.docx or upon request to Co-I [name].

The content protocol for the **music listening instruction** arm can be found here P:\CBCS\CSD CAL\Study 15 Music Training NIA\Trainer Docs\Music Listening PowerPoints.zip or upon request to the PI.

Participants will be scheduled by the trainers or study coordinator for in-lab intervention phase sessions in groups of up to 10 individuals by randomized condition. We are limited to 10 persons per class due to the physical space available for the music listening condition. The piano and music listening labs are located on the USF campus and both can accommodate 10 participants in a group intervention session. Scheduled participants will be sent an appointment letter with directions and a map (by mail if visit is 8 or more days, by email if visit is within the next 7 days). Participants will be reminded one to three days prior to the first intervention visit by telephone by a Research Assistant.

Both conditions will attend training two times a week for 10 weeks with the goal of completing a total of 20 sessions before post-testing. Participants will be encouraged to complete training two times a week without missing two or more consecutive sessions. Make up sessions will be held for each condition weekly, as needed⁵. The training phase can be extended up to a maximum of 15 weeks, if needed to complete 20 sessions. Participants will be encouraged to complete post-test regardless of intervention adherence. We will code participants as completing training if 16 or more sessions are completed (16 to 20 sessions inclusive). All training sessions must be completed within 15 weeks of training start date. The Trainers will confirm or reschedule the participant to complete an immediate post-intervention assessment within 2-60 days of their final in-lab intervention session (i.e., training completion date), or within 18 weeks of baseline if none of the the intervention phase was completed. See further details below in **Intervention Phase** and **Retention**.

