9.3 Sample Size

We expect up to 20% attrition after the initial in-person visit across the time period in which cognitive intervention study protocols will be administered. Our goal is to complete in-person screening visits for up to 450 participants in order to have up to 360 participants complete the study. We can tolerate higher rates of attrition. We require a minimum of 198 eligible participants with *at least* 99 individuals randomized to each condition (piano training, controls) to have adequate statistical power. With stratified randomization, this will result in *at least* 48 persons per MCI/no MCI subgroup.

Statistical power analysis using G*Power¹²³ in consideration of our pilot data effect sizes as well as attrition was conducted to estimate power. We will control type I error at .05 to achieve at least 80% statistical power.

To power **Specific Aim 1: To examine the efficacy of piano training to improve CAP, cognition, and everyday function among older adults**, a final n of 198 participants ($n=99$ per randomized condition) will achieve 95% power to detect a significant group x time interaction across baseline to immediate post-test, with an alpha of .05. This assumes a small effect size (f) of 0.10¹²⁴ (Cohen's f effect sizes are 0.10- small, 0.25- medium: f is roughly equivalent to $\frac{1}{2}$ of d when comparing two groups)¹²⁴.

To power **Specific Aim 2: To examine the moderating effects of MCI on intervention efficacy**, a final n of 168 will have .95 power at alpha .05 to detect medium effects ($f=.10$) for significant group x time x moderator three way interactions.

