Specific Aim 1: To examine the efficacy of piano training to improve CAP, cognition, and everyday function among older adults. We will compare changes in performance for piano training relative to control across the two measurement points (baseline, immediate post-test). We will use the PCA-derived composites of CAP and cognition, and everyday functioning as outcomes. We will use repeated measures analyses of variance within the mixed effects models, examining group as the between-subjects factor and time as the within-subjects factor. The group x time interaction will indicate whether the participants randomized to piano training change at differential rates over time relative to those randomized to the control group. This output will be obtained for each of the composite outcomes (CAP, cognition, and functional abilities). For aim 1 analyses and the composite outcomes of CAP, cognition, and everyday function, we will apply Holm-Bonferroni adjustments¹²⁵ to reduce Type I error. Specifically, the Holm-Bonferroni procedure uses a step-down process whereby p-values are sorted from lowest to highest, then the lowest p-value is used in its raw version, the second lowest p-value is multiplied by two, the third lowest p-value is multiplied by three and so on until the adjusted

p-value reaches or exceeds the pre-specified threshold for statistical significance, in our case a two-tailed p value of .05.

Intent-To-Treat Approach. We expect that some participants will not complete their intended followup according to the protocol for a variety of reasons, generating missing values. Intent-to-treat (ITT) analysis has become a widely accepted method for dealing with this issue. To maximize available information, we will employ statistical techniques that allow for the inclusion of missing data. Specifically, we will use linear mixed effects models to analyze data. This advanced analytical method allows for the inclusion of participants with missing data, so long as data are missing at random and offers flexibility with regard to the specification of the variance/covariance structure, which often leads to improved fit of the analytical model to the actual data. If there is non-ignorable missing data, we will apply pattern-mixture mixed effects models to assess the sensitivity of our findings with regard to missing data¹²⁶.

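### Training is delivered in classes within arm, but neither the sample size nor the mixed model allows for class; if change correlates within class, standard errors are too small and power is overstated.

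*Combined protocol and SAP*

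**What the plan says.** **Randomisation and delivery.** Section 5.5 randomises individuals within MCI strata: they "will be randomized in a 1:1 ratio to either piano training or the active control condition of music listening instruction". Section 5.7 then schedules "in-lab intervention phase sessions in groups of up to 10 individuals by randomized condition". Section 1.5 says that a trainer leads each group, and the programme is 20 sessions of 90 minutes. Section 6.1.2 aims for 3 to 10 people in 95% of sessions and arranges classes so that "those with MCI primarily train together within randomized condition". Section 6.3.1 describes regular weekday slots, with make-up sessions for absences.

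**Sample size.** Section 9.3 states "We will control type I error at .05 to achieve at least 80% statistical power" and sets the floor with "We require a minimum of 198 eligible participants with" 99 per condition. It says that this number "will achieve 95% power to detect a significant group x time interaction across baseline to immediate post-test", at Cohen's f = 0.10. It gives no design effect, ICC or pre-post correlation.

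**Analysis.** Section 9.6 specifies a repeated-measures mixed model, "examining group as the between-subjects factor and time as the within-subjects factor", judged against "in our case a two-tailed p value of .05". Aim 2 adds MCI status. No class or trainer term and no cluster-robust error appears in 9.6, 9.7 or 9.8. The terms reported in Table 14.2 are group, time, their interaction, hearing, visual acuity and expectations.

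**The concern.** Individual randomisation makes participants independent at allocation, but not after ten weeks in a shared class. A common trainer, pace and group dynamic can move the members' scores together. The class sits wholly inside one arm, so any such shared movement adds to the variance of the arm difference. A model with person-level repeated measures alone does not see that variance.

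At stake are the type I error of the group x time test, the width of its confidence interval, and the power on which the minimum of 198 rests. Aim 2 is exposed as well. If MCI and non-MCI participants shared classes, a common class effect would largely cancel from the MCI contrast. Because those with MCI mostly train together, it does not cancel.

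**Working it through.** **Inputs from the documents:** N = 198 (99 per arm), f = 0.10, alpha .05 two-sided, 2 time points, power 95% (9.3, 9.6); class size 3 to 10 (5.7, 6.1.2); 146 non-MCI and 52 MCI participants analysed (Table 14.3).

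**Assumed, because not stated:** class ICC for change, .01 to .10; class size m = 5, 8 or 10; pre-post correlation rho.

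**Step 1. The plan's own power.** For a within-between interaction, lambda = f² x N x 2 / (1 - rho), tested on F with 1 and 196 degrees of freedom.
- rho = .70: lambda = 0.01 x 198 x 2 / 0.30 = 13.2, power 95.1%. The stated figure reproduces.
- rho = .50: lambda = 3.96 / 0.50 = 7.92, power 80.0%.

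So the 95% needs independent participants and an unstated rho near .70.

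**Step 2. Allow for class.** The design effect is DE = 1 + (m - 1) x ICC. The correct standard error is the unadjusted one times √DE. The true alpha of the unadjusted test is 2 x (1 - Φ(1.96/√DE)). Power uses lambda / DE, with rho = .70.

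| m | ICC | DE | SE multiplier | True alpha | Power at N = 198 |
|---|---|---|---|---|---|
| 5 | .01 | 1.04 | 1.02 | 5.5% | 94% |
| 5 | .05 | 1.20 | 1.10 | 7.4% | 91% |
| 5 | .10 | 1.40 | 1.18 | 9.8% | 86% |
| 8 | .01 | 1.07 | 1.03 | 5.8% | 94% |
| 8 | .05 | 1.35 | 1.16 | 9.2% | 88% |
| 8 | .10 | 1.70 | 1.30 | 13.3% | 79% |
| 10 | .01 | 1.09 | 1.04 | 6.1% | 93% |
| 10 | .05 | 1.45 | 1.20 | 10.4% | 85% |
| 10 | .10 | 1.90 | 1.38 | 15.5% | 75% |

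At ICC 0, DE = 1 and nothing moves. Simulated unadjusted tests on change scores agree closely: 7.7% for m = 5 and 10.3% for m = 10 at ICC .05. The power column still uses person-level degrees of freedom. With about 20 classes of 10 (18 degrees of freedom), power at m = 10 is about 81% (ICC .05) and 70% (ICC .10).

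**Step 3. Aim 2.** If the 52 MCI participants analysed split evenly, there are 26 per arm. Over a pilot and five or six replicates (six or seven waves), 26/7 = 3.7 to 26/6 = 4.3, or about 4 per arm per wave. Take ICC .05, with non-MCI classes of 8 (DE 1.35), MCI classes of 4 (DE 1 + 3 x .05 = 1.15) and equal arms.
- Two-way: DE = (146 x 1.35 + 52 x 1.15) / 198 = 1.30, alpha about 8.5%.
- Three-way: DE = (1.35/73 + 1.15/26) / (1/73 + 1/26) = 1.20, alpha about 7.4%.

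With classes of 8 throughout, DE is 1.35 for both and alpha is about 9.2% for both. The three-way inflation is therefore equal or smaller in these cases.

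**Step 4. Reported results (Table 14.2), scaled by √1.45 = 1.204.** Cognition: 0.39 with SE 0.84 becomes SE 1.01, and p moves from .638 to about .70. ATTR, the smallest tabulated interaction p: SE 1.35 becomes 1.63, and p moves from .265 to about .35.

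**The case against.** The strongest reply is that the harm depends on an ICC that the documents do not give, and that it may be small. Outcomes are individual tests given by testers blind to condition (5.5, 6.1.3), not trainer ratings. Only 76% of those randomised completed post-test (section 14), so analysed clusters are smaller than the classes were. With 5 per class and ICC .01, alpha is only 5.5%. All of this stands, and it is why the point is conditional.

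Four stronger readings are tempting, and the documents do not support them.
- *That the classes are fixed and each keeps one trainer throughout.* Neither is stated. Weekly make-up sessions by condition (5.7, 6.3.1), extra sessions after a low score (6.1.2) and up to three sessions a week (6.3.1) mix participants within arm and dilute clustering.
- *That the standard errors are definitely too small.* That needs a positive ICC for change.
- *That the MCI interaction is hit harder than Aim 1.* Arm is wholly a class-level factor and MCI only mostly so; step 3 gives equal or smaller inflation. Few classes limit the degrees of freedom of a corrected test, but they do not enlarge the design effect.
- *That the trial's conclusions are in doubt.* Section 14 reports every group x time p above .194 and every MCI interaction p above .245. A class effect would generally raise them.

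Section 9.6 does mention flexible covariance structures, but in its missing-data paragraph and without reference to class.

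**Conclusion.** The omission is real: delivery is clustered within arm in both conditions, and neither 9.3 nor 9.6 allows for it. For any positive class ICC, the planned tests for Aims 1 and 2 are too liberal and the stated 95% power is too high.

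Over ICC .01 to .10, true alpha runs from about 5.5% (5 per class) to 15.5% (10 per class), and power at 198 from about 94% to 75%. These figures rest on an assumed ICC, assumed equal class sizes, stable class membership and rho = .70. With rho = .50, power starts at 80%. Make-up sessions pull towards the lower end of the inflation.

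The Aim 2 interaction is exposed to a similar or smaller degree, and it rests on few, small MCI classes. The consequence is for precision, power and control of type I error; the null findings would be expected to stand.

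**What to change.** - **Section 9.6, Aims 1 and 2:** add a random class effect on change (class-by-time), with class nested in arm and replicate, and use Satterthwaite or Kenward-Roger degrees of freedom. Define class as the one originally assigned, whatever make-up sessions were attended. Report the ICC for each composite.
- **Data:** record the assigned class as a variable. Section 5.8 mentions only attendance dates, so for the completed trial it may have to be rebuilt from the class schedules.
- **Section 9.3:** restate the power with the assumed pre-post correlation, class size, ICC and design effect.

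The cost is one variance component, some work to recover class membership, somewhat wider intervals and a less favourable stated power. With few MCI classes, the class variance may be poorly estimated for Aim 2, and the report should say so.
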